Bright Light Treatment At Home To Manage Chronic Pain In U.S. Veterans

NCT02373189

Document date: 12/23/22

Protocol for ORA# 13082603: Bright Light Treatment at Home to Manage Chronic Pain in US Veterans

[figure not shown]

Figure. A sample diagram for the 3 week pilot protocol proposed in this R34 application. This protocol is for an average 12 to 8am sleeper. There will be 4 lab visits and 3 home visits during the 3 week study. The grayed rectangles show when subjects will dim their lights at home for saliva collection, starting 30 min before the first saliva sample. Each black dot is when a saliva sample is scheduled, starting 6 h before habitual bedtime initially, thereafter 8 h before habitual bedtime to capture subsequent advances in the DLMO. The yellow rectangle indicates when the 1 h/day bright light would occur, starting at habitual wake time, possibly earlier if required to fit into the subject's daily schedule [4, 5].

Protocol

A sample protocol for this pilot study is shown in the Figure above. On Day 1 (lab visit #1) subjects will complete questionnaires, receive a wrist activity monitor, and a Personal Data Assistant (PDA; electronic diary) to record their daily pain, mood, sleep, and substance use (alcohol, caffeine, prescribed and over the counter medication, heating pads, ice packs, etc) while they sleep ad lib at home, following their usual sleep schedule. They will then undergo pain sensitivity testing (acute pain induction with forearm ischemia and heat, between noon-1pm as per our pilot). On Day 8 (lab visit #2) subjects will complete questionnaires, have their diaries and wrist actigraphy data reviewed and then will undergo pain sensitivity testing again. Following this subjects will be trained in home saliva collection, receive a kit to take home and will complete their saliva collection that night. The following morning (Day 9, home visit #1) two research staff (mixed gender team) will visit the subject in their home to set up and instruct the subjects in the bright light treatment, and collect their saliva kit and samples. Subjects will self-administer the bright light for 1 h/morning for 6 days before returning to the lab (Day 15, lab visit #3) for repeat questionnaires, review of their diaries and wrist actigraphy, pain sensitivity testing and issuing of the saliva collection kit. Research staff will again visit their homes to collect the saliva kit and samples (Day 16, home visit #2). After a further 7 days of bright light treatment, subjects will return for their last lab visit (Day 22, lab visit #4) for questionnaires, review of their diaries and wrist actigraphy, repeat pain sensitivity testing and issuing of the saliva collection kit. The following morning on Day 23 another home visit (home visit #3) will occur, and research staff will collect the light boxes, saliva kit, samples, and wrist monitors. The PDAs for electronic diaries will be left with the subject. During a 1 month follow up after cessation of the bright light treatment, subjects will continue to report their pain, mood and sleep once a day on the electronic diaries (once a day only to reduce burden and improve compliance). At the end of the follow up staff will collect the PDAs with electronic diaries during a final home visit.

Amendment 3: there will be 1 more lab visit, approximately 2 weeks into the 30 day follow up to enable us to download data from the e-diary. We will schedule this extra lab visit at a date and time convenient to the veteran to reduce their burden.

Bright Light Treatment At Home To Manage Chronic Pain In U.S. Veterans

NCT02373189

Document Date: 12/23/22

Data Analysis

Aim 1. To determine the feasibility and acceptability of bright light treatment in a sample of US veterans (n=30) experiencing chronic low back pain. For Aim 1 we will track the number of US veterans who express interest in the study, the number that meet our inclusion criteria, the number that enroll, the number of mornings that bright light is self-administered and the duration of the exposure, and we will collect treatment expectancy and treatment satisfaction ratings. Hypothesis 1: We expect reasonable feasibility in that (i) we will be able to enroll 2 US veterans per month, (ii) $\geq 75\%$ of those enrolled self-administer at least 30 mins of morning bright light on at least 50% of treatment days (this light should still be somewhat effective, as per winter depression studies [125, 126, 131]). Research Strategy Page 54 Contact PD/PI: [name] Hypothesis 2: We expect reasonable acceptability in that (i) at least 1 in 4 US veterans who are eligible for the study agree to participate, (ii) average expectancy rating at start of bright light treatment is $\geq 6/10$, (iii) the attrition rate is $\leq 30\%$, and (iv) average treatment satisfaction at end of bright light treatment is $\geq 6/10$. Aim 2. To examine the effects of 6 days and 13 days of bright light treatment on chronic pain intensity and sensitivity in US veterans (improved PTSD symptoms, mood and sleep are secondary outcomes).

For Aim 2 we will plot daily diary ratings of pain intensity expressed as percentage change from baseline pain intensity (mean intensity over the 7 days of baseline). The point where the mean change for the whole sample achieves 30% (“moderately clinically meaningful effect” p.239, [137]) will reveal a potential candidate for an optimal treatment dose. We will also examine pain sensitivity (ischemia, heat) changes over the 4 lab visits. Hypothesis 3: We expect (i) a $\geq 30\%$ reduction in pain intensity ratings and (ii) a $\geq 30\%$ reduction in pain sensitivity (ischemia and thermal pain) by the 13th day of morning bright light treatment. As a preliminary analysis, we will examine these data with a within-subjects ANOVA to determine: a) effect size of change over 13 days of treatment; b) statistical significance of this change; c) whether there is significant non-linearity indicating that response to treatment reached a plateau. In an effort to understand a plateau effect, we will use a piecewise linear mixed model with a fixed change point occurring at the 30% change level. Random effects for time before the change point and time after change point will be included in the model. We will use graphical analyses to investigate violations of the model assumption. Secondary analyses for daily ratings of mood and sleep will be conducted similarly. For additional secondary analyses involving PTSD, depressive and anxiety symptoms, and sleep questionnaires, we will subject data to within-subjects ANOVAs to determine: a) effect sizes of changes over 13 days of treatment; b) statistical significance of these changes; c) whether there is significant non-linearity indicating that treatment response plateaued.

Aim 3. To determine time course of decay of treatment response (decreased pain intensity) after cessation of light treatment. For Aim 3, we will plot daily diary ratings of pain intensity expressed as percentage change from the mean of pain ratings over the last 3 days of bright light treatment. The point where the mean change for the whole sample achieves 20% (less than a “moderate” decrease [137]) will reveal a potential candidate time for a maintenance dose of bright light. Second, we will subject these data to a within-subjects ANOVA to determine: a) effect size of erosion over 4 weeks of follow-up; b) statistical significance of this change. A change point modeling strategy similar to Aim 2 will be used here, but the change point will be set at a 20% level rather than a 30% level. Secondary analyses involving daily diary ratings of sleep and mood will be conducted as described above. Hypothesis 1: A mean increase of 20% in pain ratings is expected to occur within the first week post treatment (as per winter depression studies [125, 126, 131]). Hypothesis 2: Pain intensity is expected to return to baseline by 1 month post treatment (as per winter depression studies [125, 126, 131]).

We will also examine effects of other factors on treatment response. We will determine whether analyses must be adjusted for confounding factors including but not limited to age, BMI, race/ethnicity, employment, physical workload, any comorbidity (including depression and anxiety), history of traumatic brain injury, time from onset of chronic pain, current psychotropic and analgesic medications, and other treatments being received for chronic pain and/or PTSD. These analyses may involve treating these factors as time-varying covariates. We will also determine whether key factors moderate treatment response. We plan to test whether men or women

and those with low vs. high psychiatric symptoms (e.g., PTSD) show evidence of differential treatment response. These analyses will involve testing Sex or Psychiatric Symptom x Time interactions on pain intensity during and following treatment. In other exploratory analyses we will examine the correlations between change in DLMO and DLMO to midpoint of sleep interval and change in pain, mood and sleep.

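### Satisfaction is rated only at the end of light treatment, with no rating planned for people who stop early, so the 6/10 criterion can be met while the mean among all who started light is below 6

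*SAP*

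**What the plan says.** In the SAP, Aim 1, Hypothesis 2 sets four expectations for acceptability. Three matter here:

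- (ii) "average expectancy rating at start of bright light treatment" is to be at least 6/10.
- (iii) The condition beginning "the attrition rate is" sets a ceiling of 30%.
- (iv) "average treatment satisfaction at end of bright light treatment" is to be at least 6/10.

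On data collection, the SAP says only that "we will collect treatment expectancy and treatment satisfaction ratings". It gives no analysis set for the mean, no rule for missing ratings and no scale minimum, and it does not tie attrition to a stage of the study. By contrast, the adherence criterion in Hypothesis 1 (ii) does name its denominator: everyone enrolled.

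In the Protocol's description of study visits, light starts after a baseline week, at the Day 9 home visit. The last questionnaires of the treatment period are at lab visit #4 on Day 22, and staff collect the light boxes on Day 23. A one-month diary follow-up comes after that. No assessment is described for a subject who stops light before Day 22.

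**The concern.** Expectancy is asked before anyone can be lost during treatment. Satisfaction is asked after those losses. A low opinion of the treatment is one plausible reason for giving it up, so whether a rating is missing may depend on what the rating would have been. If so, the mean over those still present is shifted towards a pass.

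Criterion (iii) limits how many ratings can be missing, but it does not correct the mean, and attrition of exactly 30% satisfies it. Acceptability is one of the two conclusions that Aim 1 is meant to deliver. The pilot could report that the satisfaction target was met when the people who were given the light did not, on average, reach it.

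**Working it through.** The plan gives no calculation for this criterion, so there is no figure to reproduce. The check is a weighted mean.

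**Inputs from the documents**
- Sample of 30 (SAP, Aim 1).
- Attrition of at most 30%, so at most 0.30 × 30 = 9 lost (Hypothesis 2 (iii)).
- Satisfaction threshold of 6 (Hypothesis 2 (iv)).
- Adherence: at least 75% of those enrolled use the light on at least half of treatment days (Hypothesis 1 (ii)). This means 0.75 × 30 = 22.5, so 23 people. Half of 13 days is 6.5, so 7 days.

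**Assumptions**
- The 30 are those enrolled.
- Completers average exactly 6.0.
- Leavers would have averaged *s* = 0, 3 or 5. The documents give no information on *s*.
- The timing of losses is as stated in each case.

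**Formula.** With *c* people finishing treatment and *k* stopping during it, the all-starter mean is (6*c* + *sk*)/(*c* + *k*). Equivalently, the shortfall below 6 is the fraction of starters who stop, multiplied by (6 − *s*).

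**Case A, the extreme: all 30 start and all 9 losses fall within treatment** (*c* = 21, *k* = 9).
(126 + 9*s*)/30 = 4.2, 5.1, 5.7.
For an all-starter mean of 6.0, completers would have to average (180 − 9*s*)/21 = 8.57, 7.29, 6.43.

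**Case B: 7 losses, all before 7 days of light use** (*c* = 23, *k* = 7). If leavers this early cannot count as adherent, 7 is the most that still leaves 23 adherent people.
(138 + 7*s*)/30 = 4.6, 5.3, 5.8.

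**Case C: 9 losses split 3/3/3 across baseline, treatment and follow-up.** There are 27 starters, of whom 24 finish treatment (*c* = 24, *k* = 3). The three follow-up losses have already given a rating.
(144 + 3*s*)/27 = 5.33, 5.67, 5.89.

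**Case D: no loss during treatment, or *s* = 6.** The shortfall is zero.

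| Case | Starters | Stop during treatment | *s* = 0 | *s* = 3 | *s* = 5 |
|---|---|---|---|---|---|
| A | 30 | 9 | 4.2 | 5.1 | 5.7 |
| B | 30 | 7 | 4.6 | 5.3 | 5.8 |
| C | 27 | 3 | 5.33 | 5.67 | 5.89 |

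In all three cases criteria (iii) and (iv) are met. The adherence criterion can be met too. In case A it needs all 21 completers to be adherent, plus 2 leavers who had used the light on at least 7 of the 13 days.

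**The case against.** Several objections are fair.

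- **Completer-only averaging is not stated.** A reader might infer that the SAP deliberately restricts criterion (iv) to completers. It does not say so, and the end of treatment could mean each subject's own last day. This stands as a limit on the claim. But no rating at an individual's own end is scheduled, so following the visits as described leaves early stoppers unrated.
- **Timing matters.** Case A puts every loss inside the 13 treatment days and both criteria exactly on their limits. Losses in the baseline week leave no starter to average, and losses in follow-up come after the rating. This stands, and it is why case A is only an extreme.
- **The adherence criterion is a partial safeguard.** Nine people leaving before 7 days of use would leave at most 21/30 = 70% adherent, and that criterion would fail. This stands, but case B passes, and later leavers escape the check.
- **The reason for leaving is unknown.** Pain testing, saliva collection, visits and diaries are also burdens, and someone leaving because of them need not dislike the light. This stands: low ratings among leavers are an assumption.
- **Attrition is reported beside satisfaction, and including leavers partly counts it twice.** The criteria are descriptive, with no stop/go rule attached. Pairing retention with satisfaction among those treated is defensible, which is a reason to keep the completer mean in the report. But the attrition figure says how many left, not what they thought of the treatment.
- **The SAP text looks like an extract from a grant application.** A withdrawal procedure may exist elsewhere. It is not in these documents.

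**Conclusion.** The concern holds in a limited form. As written, early stoppers would go unrated in practice, and criteria (iii) and (iv) can both be met while the mean among all starters is below 6/10. The shortfall runs from nothing to 1.8 points (6.0 − 4.2), and the top of that range needs all 9 losses during treatment and leavers rating 0. With 7 early losses it is 0.2 to 1.4 points, and with an even split of losses 0.11 to 0.67, for leaver ratings of 5 down to 0.

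A reader might go further and conclude that the criterion will be passed misleadingly, or that the all-starter mean would be far below 6. The documents do not support that. They say nothing about how leavers would rate the light or when losses would fall, and the gap vanishes if leavers are equally satisfied or leave outside treatment. The point is that the plan could not tell these situations apart, because the ratings needed would not have been collected.

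**What to change.** 1. Ask the same satisfaction item whenever a subject stops light early, for example when the light box is collected.
2. State in the SAP that criterion (iv) is the mean over all who started light, using the rating given at each subject's own end of treatment. Report the completer mean beside it, with both denominators.
3. For starters with no rating, show the mean with the scale minimum substituted, as a sensitivity bound and not as the deciding result. State that minimum: in case A with no leaver rated, the bound is 4.2 if it is 0 and (126 + 9)/30 = 4.5 if it is 1.
4. Report attrition by stage (before light, during light, follow-up), so that readers can see how much of it bears on this mean.

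The cost is one question at stopping and a few sentences in the SAP. Some who stop may not answer, which is why the bound is needed, and the figure may be slightly less favourable.

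### Aim 2 names 6 and 13 days of light, but no 6-day or 6-versus-13-day contrast with an interval is planned, and reading significant non-linearity as a plateau is unreliable

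*SAP*

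**What the plan says.** The SAP's Data Analysis section gives the Aim 2 objective as "To examine the effects of 6 days and 13 days of bright light treatment on chronic pain intensity and sensitivity in US veterans". The Protocol's schedule supplies a measurement at each duration: "Subjects will self-administer the bright light for 1 h/morning for 6 days before returning to the lab (Day 15, lab visit #3"), and then "After a further 7 days of bright light treatment, subjects will return for their last lab visit (Day 22, lab visit #4"). Questionnaires and pain sensitivity testing are done at both visits, and also on Days 1 and 8 before treatment.

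The Aim 2 analysis text attaches numbers to one duration only:

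- Hypothesis 3 expects falls of at least 30% in pain intensity and sensitivity "by the 13th day of morning bright light treatment".
- The within-subjects ANOVA for pain is to give "effect size of change over 13 days of treatment; b) statistical significance of this change".
- The ANOVAs for PTSD, depressive and anxiety symptoms and the sleep questionnaires are to give "effect sizes of changes over 13 days of treatment".

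Both ANOVA statements add a test of non-linearity and take a significant result as a sign that response has levelled off. The same text also plans a daily course for diary pain ("we will plot daily diary ratings of pain intensity expressed as percentage change from baseline pain intensity"), an examination of ischemia and heat sensitivity across the four lab visits, and a piecewise linear mixed model whose change point sits where the change reaches 30%.

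**The concern.** The objective asks about two durations and the analysis quantifies one. Someone following the SAP could report an overall 13-day change and a curvature p-value for each outcome, and still not state how much had changed after 6 days, how much the second week added, or how uncertain either figure is.

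This matters most for the outcomes measured only at lab visits: pain sensitivity, PTSD, depressive and anxiety symptoms, and the sleep questionnaires. They have no daily course to fall back on. For them the only stated rule separating early from late response is the non-linearity test, so an error in reading that test goes straight into the conclusion about time course. Time course is an output this pilot wants, since Aim 2 looks for a candidate treatment duration to take forward.

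**Working it through.** **1. Do the visits fall at 6 and 13 days?** The Protocol gives 6 days of light before lab visit #3 and a further 7 before visit #4: 6 + 7 = 13. The count is the same whether the first light morning is Day 9 (Days 9–14, then 15–21) or Day 10 (Days 10–15, then 16–22). The SAP's 13 days is reproduced.

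**2. Which durations carry an estimate or hypothesis in Aim 2?** Three statements name a duration: Hypothesis 3, the pain effect size and the questionnaire effect sizes. All three say 13 days and none says 6.

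**3. How different could the 6-day result be for the same 13-day result?** Take the hypothesised 30% fall at 13 days.

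- Linear course: 30 × 6/13 = 13.8% at 6 days, so the second week adds 30 − 13.8 = 16.2 points.
- Early plateau: 30% at 6 days, so the second week adds 0.

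An effect size computed as the 13-day endpoint change is 30% in both cases.

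**4. Can the non-linearity test separate these patterns?** The SAP does not say which visits or which polynomial terms enter the test, so both obvious choices are shown. Values are illustrative percentage changes from baseline.

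Three visits (Days 8, 15, 22), quadratic weights (1, −2, 1):

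| Pattern | Values | Contrast |
|---|---|---|
| Plateau by Day 15 | 0, −30, −30 | 0 + 60 − 30 = +30 |
| Reversal | 0, −30, 0 | 0 + 60 + 0 = +60 |
| Late onset | 0, 0, −30 | 0 + 0 − 30 = −30 |

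All three are non-zero, so given enough precision all three would be significant. Only the first is a plateau.

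Four equally spaced visits (Days 1, 8, 15, 22), flat baseline, quadratic weights (1, −1, −1, 1):

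| Pattern | Values | Contrast |
|---|---|---|
| Perfect 6-day plateau | 0, 0, −30, −30 | 0 − 0 + 30 − 30 = 0 |
| Steady decline, no plateau | 0, 0, −15, −30 | 0 − 0 + 15 − 30 = −15 |

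Here the quadratic term misses the plateau and responds to a steady decline, because the flat baseline itself bends the curve. Adding the cubic term, weights (−1, 3, −3, 1), does not rescue the reading. It gives 0 + 0 + 90 − 30 = +60 for the plateau and 0 + 0 + 45 − 30 = +15 for the steady decline, so both patterns still count as non-linear.

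**5. What precision would direct contrasts have?** The 95% CI half-width for a paired difference, in SDs of that difference, is t(0.975, n−1)/√n.

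- n = 30 (SAP sample size): 2.045/5.477 = 0.373.
- n = 21 (30 × 0.70, the SAP's 30% attrition ceiling): 2.086/4.583 = 0.455.

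**The case against.** A reader might infer that the 6-day response is never estimated. The documents do not support that. The daily plot shows the mean percentage change in diary pain on treatment day 6, and the search for the day on which that mean reaches 30% addresses early response more finely than a 6-versus-13-day comparison. The four-visit sensitivity analysis includes Day 15. The piecewise model has slopes on either side of its change point, from which a fitted day-6 value and standard error can be derived. This part of the objection stands. What remains is that no 6-day or second-week figure with an interval is named for reporting, and that neither the plot nor the piecewise model reaches the questionnaires.

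A reader might also infer that the planned effect size could not tell a linear course from an early plateau. That holds only for an endpoint difference. An omnibus ANOVA effect size would differ: the sum of squares about the mean is about 451 for falls of 0, 13.8 and 30, against 600 for 0, 30 and 30. With a second baseline at 0 the figures are about 611 and 900. Even so, an omnibus figure does not say where the change occurred.

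Nor do the documents say that lab visit #3 exists to compare durations. It also serves diary and actigraphy review and issue of the saliva kit.

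Two further points are fair. Visit means, if shown, would let a reader see whether curvature reflects plateau, reversal or late onset, but the SAP's stated rule relies on significance. And the SAP specifies no confidence interval for 13 days either, so that omission is not peculiar to day 6. Finally, this is a pilot without a control group and the ANOVA is labelled preliminary, which limits the severity.

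**Conclusion.** The point holds as a specification gap together with an unreliable decision rule. Aim 2 names two durations. Its effect sizes and hypothesis are all for 13 days, and the 6-day response is available only descriptively or by derivation. The plateau reading is the more substantive part, because significant curvature also arises from late onset or reversal, and a four-visit quadratic can be exactly zero when the plateau is perfect.

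The size of what is left open is illustrated by 13.8% against 30% at 6 days for the same 13-day fall. That range assumes the hypothesised 30% is reached and compares two idealised courses. The contrast values assume a flat baseline and the patterns shown; they concern expected values, not the power of the test. Severity is minor to moderate: no design feature or sample size is affected, and the statement is confined to Aim 2, since Aims 1 and 3 have their own hypotheses.

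**What to change.** Amend the Aim 2 analysis text as follows.

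- **Pain sensitivity and questionnaires:** from the planned repeated-measures model, report Day 15 minus Day 8, Day 22 minus Day 8 and Day 22 minus Day 15, each with a 95% CI.
- **Diary pain:** report the change from the baseline week at treatment day 6 and at treatment day 13, and the difference between them, with 95% CIs. Means of the 3 days ending on each would match the window Aim 3 already uses; another window is acceptable if stated in advance.
- **Plateau:** judge it from the size and CI of the second-week change, and drop the rule that significant non-linearity indicates a plateau. If the non-linearity test is kept, state which visits and terms it uses and present it beside the visit means.

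The cost is a few sentences and contrasts from models and data already planned. The downside is two more estimates per outcome, with half-widths of about 0.37 SD of the paired difference at n=30 and 0.46 SD at n=21. At that precision only a fairly large further fall could be excluded, so the contrasts should be labelled descriptive.

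### The 30% and 20% points are read from a plotted daily mean with no rule for dropouts or missed diary days, so dropout related to response would bias both readings

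*SAP*

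**What the plan says.** In the SAP (Data Analysis, Aim 2) the diary data are first shown as a curve: "we will plot daily diary ratings of pain intensity expressed as percentage change from baseline pain intensity", where baseline is the mean of the seven baseline days. The reading taken from it is "The point where the mean change for the whole sample achieves 30" per cent, which "will reveal a potential candidate for an optimal treatment dose". Aim 3 repeats the device for follow-up, with pain expressed relative to the mean of the final three treatment days. There, "The point where the mean change for the whole sample achieves 20" per cent gives a candidate time for a maintenance dose.

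Aim 1 concerns feasibility "in a sample of US veterans (n=30) experiencing chronic low back pain". Its Hypothesis 2, item (iii), counts attrition of up to 30% as acceptable, without saying over what period.

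Two model analyses follow the plot. One is a within-subjects ANOVA for effect size and significance. For the other, aimed at a plateau, the SAP states: "we will use a piecewise linear mixed model with a fixed change point occurring at the 30% change level". Aim 3 uses the same approach at 20%. Neither document gives an analysis set, a rule for missed diary days or dropouts, or a sensitivity analysis for dropout.

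**The concern.** A mean plotted from ratings can use only the ratings that exist. With no rule, the curve on a given day describes whoever reported that day, although the SAP labels it as the whole sample. If people who benefit little are more likely to stop, the group being averaged comes to contain more responders. The Aim 2 curve then reaches 30% sooner than it would with everyone included, or reaches it when the full group never does.

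Two outputs depend directly on these curves: the candidate dose point and the candidate maintenance time. Hypothesis 3(i) may depend on them too, since the SAP does not say which quantity decides it. There is no control arm in which selective loss might show up.

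The planned models do not clearly repair this. In the piecewise model the 30% or 20% point is an input, so if it is taken from the plot, any bias in the plot is carried into the model. A within-subjects ANOVA in its standard form uses only complete subjects, so it too would describe those who stayed.

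**Working it through.** The documents give no power, precision or attrition-adjusted figure, so there is none to reproduce.

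**Inputs from the documents.** n = 30; attrition up to 30%, so up to 0.30 × 30 = 9 lost and 21 remaining; thresholds of 30% (Aim 2) and 20% (Aim 3). Lab visit 4 is on study Day 22, after 13 days of light. The last home visit of the treatment phase is Day 23, and a 30-day follow-up takes the study to about Day 23 + 30 = 53.

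**Assumed, not in the documents.** The response of those lost, the timing of loss, and the SD and correlation used below.

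**Identity.** Whole-sample mean = (1 − d) × mean of those reporting + d × mean of those lost, where d is the fraction lost by the reading day.

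**Aim 2, plotted reduction 30%, all attrition before the reading day (d = 0.30).**

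| Mean reduction in those lost | Whole-sample reduction |
|---|---|
| 0% | 0.70 × 30 + 0.30 × 0 = 21.0% |
| 10% | 21.0 + 0.30 × 10 = 24.0% |
| 13.3% | 21.0 + 0.30 × 13.3 = 25.0% |
| 20% | 21.0 + 0.30 × 20 = 27.0% |
| 30% (same as stayers) | 21.0 + 0.30 × 30 = 30.0% |
| 10% worse | 21.0 − 0.30 × 10 = 18.0% |

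**Aim 2, 30% attrition accruing evenly to Day 53.** By Day 22, d = 0.30 × 22/53 = 0.125. With 0% change in those lost, the whole-sample reduction is 0.8755 × 30 = 26.3%. With a 13.3% reduction in those lost, it is 26.3 + 0.1245 × 13.3 = 27.9%.

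**Cross-check by selection.** If the 70% retained are selected on something correlated ρ with response, the lift is ρ × SD × φ(z₀.₃₀)/0.70. Here φ(z₀.₃₀)/0.70 = 0.497. With SD 30 points, ρ = 0.3 gives 4.5 points and ρ = 0.5 gives 7.5 points; ρ = 0 gives none.

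**Aim 3, plotted rise 20%, d = 0.30.** If those lost had no rise, the whole-sample rise is 0.70 × 20 = 14%, and the 20% point is read too early. If those lost had risen 40%, it is 14 + 0.30 × 40 = 26%, and the point is read too late. Anyone lost before the final three treatment days has no reference value and cannot enter this curve.

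**Simulation at treatment day 13.** Averages over 60 trials of n = 30, assuming 70% responders reaching about −36%, 30% non-responders, and dropout driven by the last three observed ratings unless stated:

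| Setting | True | Reporting only | Mixed model | Leavers at 0% |
|---|---|---|---|---|
| 34% attrition, moderate dependence | −25.2 | −29.3 | −25.0 | −19.3 |
| 16% attrition, stronger dependence | −25.2 | −27.9 | −25.3 | not run |
| 31% attrition, unrelated to response | −24.9 | −24.6 | not run | not run |

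With day entered as a category, a similar simulation (31% rating-related attrition) gave true −24.7, reporting only −29.3 and model −23.5. Some of those fits produced convergence warnings.

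**The case against.** The opposing case has real force on size and direction.

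- **Silence is not a rule.** The SAP names the whole sample and does not exclude imputation or a model-based mean. That averaging will be over reporters only is the default reading, not a stated plan.
- **A reader might infer that the curve could fall to 30% with nobody improving.** The documents do not support that. The curve is change from baseline; if every subject's change were zero or worse, no subset could average a reduction. Selection can only magnify a reduction that some subjects have.
- **A reader might take 21% to 25% as the size of the bias, or 21% as its limit.** Both ends need all 30% attrition before the reading day, and a mean reduction of only 0% to 13% in leavers. Neither is in the documents. Nor is 21% a bound, because leavers could get worse.
- **A reader might infer that every reading moves in the plan's favour.** It need not. Dropout unrelated to response gives no systematic shift, and loss of improvers reverses it. In Aim 3, losing those whose pain returned would delay the 20% point, which works against the SAP's own hypothesis of a 20% rise within the first week.
- **The simulation is not independent support for the model.** Dropout was made to depend on observed ratings, which is the condition that suits a mixed model.
- **The bias is small beside the noise.** With an assumed SD of 30 points the standard error is 30/√30 = 5.5 for 30 subjects and 30/√21 = 6.5 for 21. A shift of 29.3 − 24.7 = 4.6 points is under one standard error.
- **The stakes are those of a pilot.** The outputs are candidates, and the ANOVA is called preliminary.

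These points limit the claim but do not remove it. Two outputs rest on a mean whose membership is undefined, and the planned piecewise model takes the threshold as given. Large sampling error is a reason to attach an interval, not to accept an avoidable bias.

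**Conclusion.** The concern holds as a conditional one: if dropout is related to response, a raw daily mean is biased, and the plan has nothing in place to prevent or reveal it. For Aim 2 the size is between nothing and about 9 points (30 − 21) in the scenarios where leavers did no worse than no change. It is about 2 to 4 points (30 − 27.9 to 30 − 26.3) if attrition accrues evenly through follow-up and leavers had a 0% to 13% reduction. For Aim 3 neither size nor direction can be fixed in advance, and early leavers are excluded by construction. Confidence is medium, because the pattern of dropout is unknown. This should be changed, as a better method is available at little cost, but it does not by itself invalidate the pilot.

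**What to change.** Fit a mixed model to the daily ratings, including the baseline week, of everyone who started light. Enter day as a category (or a smooth term), with a random intercept and slope per subject and no preset change point. The planned piecewise model cannot serve here: reading the 30% crossing from a model that fixes it would be circular.

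Compute percentage change from the model means, relative to the baseline week for Aim 2 and to the final three treatment days for Aim 3. Read the 30% and 20% points, and Hypothesis 3(i), from that curve with a confidence interval, and allow the answer that the threshold was not reached.

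Also:
- state how missed diary days are handled and over what period attrition is counted;
- print the number of subjects contributing under each day of the plot;
- report one sensitivity analysis: leavers at 0% change for Aim 2, and return to baseline for Aim 3 among those who have a reference value.

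The cost is SAP wording and one additional model of a familiar class; no new data are needed. There are four drawbacks. The reported response may be a few points smaller. The model assumes that dropout is explained by observed ratings, which is why the sensitivity analysis is needed. That analysis is deliberately pessimistic (−19.3 against a true −25.2 in the simulation) and should not be read as an estimate. With 30 subjects the day-as-category form may not converge cleanly, so the SAP should name the smooth-term version as the fallback.
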